6.6.1.2 Medical Outcome Short Form Health Survey (SF-36) Version 2 (4-week recall period)

The SF-36 is a widely used and extensively studied instrument to measure health-related quality of life (HRQoL) among healthy subjects and patients with acute and chronic conditions. It consists of eight subscales that can be scored individually: Physical Functioning, Role-Physical, Bodily Pain, General Health, Vitality, Social Functioning, Role-Emotional, and Mental Health (Ware 1993). Two overall summary scores, the Physical Component Summary (PCS) and the Mental Component Summary (MCS) also can be computed (Ware 1994). The SF-36 has proven useful in monitoring general and specific populations, comparing the relative burden of different disease, differentiating the health benefits produced by different treatments, and in screening individual subjects. The purpose of the SF-36 in this study is to assess the HRQoL of subjects. Given the nature of this disease and the 4-weekly assessment, the SF-36 version 2, with a 4-week recall period, will be used in this study.

6.6.1.3 Beck Depression Inventory (BDI)-II

The BDI-II is a 21-item questionnaire that assesses severity of depression. Each item is scored from 0 to 3. The total score is categorized into 4 severity grades: minimal depression (0 – 13), mild depression (14 – 19), moderate depression (20 – 28), and severe depression (29 – 63) (Beck 1996).

The questionnaire takes approximately 10 minutes to complete. Patients will be asked to complete this in their eDiary during their scheduled clinic visit, at the frequency outlined in Table 6-1. The recall period is the preceding two weeks, including the day of completion.

[REDACTED]

7 Safety monitoring

7.1 Adverse events

An adverse event (AE) is any untoward medical occurrence (e.g., any unfavorable and unintended sign [including abnormal laboratory findings], symptom or disease) in a patient or clinical investigation patient from randomization (Visit 101) until the end of study visit (16 weeks after the last IMP injection). Any events occurring during the Screening and Baseline Epochs and conditions that were already present at the time of informed consent should be documented as medical history. An AE may or may not be temporally or causally associated with the use of a medicinal (investigational) product.

In addition, all reports of intentional misuse and abuse of the product are also considered an adverse event irrespective if a clinical event has occurred.

The occurrence of adverse events must be sought by non-directive questioning of the patient at each visit during the study. Adverse events also may be detected when they are volunteered by the patient during or between visits or through physical examination findings, laboratory test findings, or other assessments.

Abnormal laboratory values or test results constitute adverse events only if they fulfill at least one of the following criteria:

- they induce clinical signs or symptoms,
- they are considered clinically significant,
- they require therapy.

Clinically significant abnormal laboratory values or test results must be identified through a review of values outside of normal ranges/clinically notable ranges, significant changes from baseline or the previous visit, or values which are considered to be non-typical in patient with underlying disease. Investigators have the responsibility for managing the safety of individual patient and identifying adverse events. Alert ranges for laboratory and other test abnormalities are included in Appendix 1.

Adverse events must be recorded in the Adverse Events eCRF under the signs, symptoms or diagnosis associated with them, accompanied by the following information:

- the severity grade
 - mild: usually transient in nature and generally not interfering with normal activities
 - moderate: sufficiently discomforting to interfere with normal activities
 - severe: prevents normal activities
- its relationship to the study treatment
 - Yes
 - No

- its duration (start and end dates) or if the event is ongoing an outcome of not recovered/not resolved must be reported.
- whether it constitutes a serious adverse event (SAE - See Section 7.2 for definition of SAE) and which seriousness criteria have been met.
- action taken regarding [investigational] treatment

If the event is due to lack of efficacy or progression of underlying illness (i.e. progression of the study indication) the assessment of causality will usually be 'Not suspected'. The rationale for this guidance is that the symptoms of a lack of efficacy or progression of underlying illness are not caused by the trial drug, they happen in spite of its administration and/or both lack of efficacy and progression of underlying disease can only be evaluated meaningfully by an analysis of cohorts, not on a single subject.

All adverse events must be treated appropriately. Treatment may include one or more of the following:

- Dose not changed
- Dose Reduced/increased
- Drug interrupted/withdrawn
- its outcome (not recovered/not resolved; recovered/resolved; recovering/resolving, recovered/resolved with sequelae; fatal; or unknown)

Adverse events (including lab abnormalities that constitute AEs) should be described using a diagnosis whenever possible, rather than individual underlying signs and symptoms.

Once an adverse event is detected, it must be followed until its resolution or until it is judged to be permanent, and assessment must be made at each visit (or more frequently, if necessary) of any changes in severity, the suspected relationship to the study drug, the interventions required to treat it, and the outcome.

Information about common side effects already known about the investigational drug can be found in the Investigator Brochure (IB). This information will be included in the patient informed consent and should be discussed with the patient during the study as needed. Any new information regarding the safety profile of the medicinal product that is identified between IB updates will be communicated as appropriate, e.g., via an Investigator Notification or an Aggregate Safety Finding. New information might require an update to the informed consent and has then to be discussed with the patient.

The investigator must also instruct each patient to report any new adverse event (beyond the protocol observation period) that the patient, or the patient's personal physician, believes might reasonably be related to study treatment. This information must be recorded in the investigator's source documents; however, if the AE meets the criteria of an SAE, it must be reported to Novartis.

7.2 Serious adverse events

7.2.1 Definition of SAE

An SAE is defined as any adverse event [appearance of (or worsening of any pre-existing)] undesirable sign(s), symptom(s) or medical condition(s) which meets any one of the following criteria:

- is fatal or life-threatening
- results in persistent or significant disability/incapacity
- constitutes a congenital anomaly/birth defect
- requires inpatient hospitalization or prolongation of existing hospitalization, unless hospitalization is for:
 - routine treatment or monitoring of the studied indication, not associated with any deterioration in condition
 - elective or pre-planned treatment for a pre-existing condition that is unrelated to the indication under study and has not worsened since signing the informed consent
 - treatment on an emergency outpatient basis for an event not fulfilling any of the definitions of a SAE given above and not resulting in hospital admission
 - social reasons and respite care in the absence of any deterioration in the patient's general condition
- is medically significant, e.g. defined as an event that jeopardizes the patient or may require medical or surgical intervention to prevent one of the outcomes listed above .

All malignant neoplasms will be assessed as serious under “medically significant” if other seriousness criteria are not met.

Life-threatening in the context of a SAE refers to a reaction in which the patient was at risk of death at the time of the reaction; it does not refer to a reaction that hypothetically might have caused death if it were more severe (please refer to Annex IV, ICH-E2D Guideline).

Medical and scientific judgment should be exercised in deciding whether other situations should be considered serious reactions, such as important medical events that might not be immediately life threatening or result in death or hospitalization but might jeopardize the patient or might require intervention to prevent one of the other outcomes listed above. Examples of such events are intensive treatment in an emergency room or at home for allergic bronchospasm, blood dyscrasias or convulsions that do not result in hospitalization or development of dependency or abuse (please refer to Annex IV, ICH-E2D Guideline).

Any suspected transmission via a medicinal product of an infectious agent is also considered a serious adverse reaction.

7.2.2 SAE reporting

To ensure patient safety, every SAE, regardless of causality, occurring after the patient has provided informed consent and until the completion of the Follow-Up Epoch (8 weeks after the

last IMP injection) must be reported to Novartis within 24 hours of learning of its occurrence. Any SAEs experienced after the completion of the Follow-Up Epoch should only be reported to Novartis if the investigator suspects a causal relationship to study treatment.

All follow-up information for the SAE including information on complications, progression of the initial SAE and recurrent episodes must be reported as follow-up to the original episode within 24 hours of the investigator receiving the follow-up information. An SAE occurring at a different time interval or otherwise considered completely unrelated to a previously reported one must be reported separately as a new event.

Information about all SAEs is collected and recorded on the Serious Adverse Event Report Form; all applicable sections of the form must be completed in order to provide a clinically thorough report. The investigator must assess the relationship of each SAE to study treatment, complete the SAE Report Form in English, and submit the completed form within 24 hours to Novartis. Detailed instructions regarding the submission process and requirements for signature are to be found in the investigator folder provided to each site.

Follow-up information is submitted as instructed in the investigator folder. Each re-occurrence, complication, or progression of the original event must be reported as a follow-up to that event regardless of when it occurs. The follow-up information should describe whether the event has resolved or continues, if and how it was treated, whether the blind was broken or not, and whether the patient continued or withdrew from study participation.

If the SAE is not previously documented in the Investigator's Brochure or Package Insert (new occurrence) and is thought to be related to the study treatment a Drug Safety and Epidemiology Department associate may urgently require further information from the investigator for health authority reporting. Novartis may need to issue an Investigator Notification (IN) to inform all investigators involved in any study with the same study treatment that this SAE has been reported. Suspected Unexpected Serious Adverse Reactions (SUSARs) will be collected and reported to the competent authorities and relevant ethics committees in accordance with EU Guidance 2011/C 172/01 or as per national regulatory requirements in participating countries.

Migraine days including migraine-related events (underlying disease) which meet SAE-definition (e.g. hospitalization) should be reported on the relevant eCRF pages instead of SAE form unless, in the judgement of the investigator, a migraine attack is unusually severe or unexpected and warrants specific notification as an SAE.

7.3 Liver safety monitoring

To ensure patient safety and enhance reliability in determining the hepatotoxic potential of an investigational drug, a standardized process for identification, monitoring and evaluation of liver events has to be followed.

The following two categories of abnormalities/adverse events have to be considered during the course of the study (irrespective of whether classified/reported as (S)AE):

- Liver laboratory triggers, which will require repeated assessments of the abnormal laboratory parameter

- Liver events, which will require close observation, follow-up monitoring and completion of the standard base liver eCRF pages

Please refer to Table 13-1-Appendix 2 for complete definitions of liver laboratory triggers and liver events.

Every liver laboratory trigger or liver event as defined in Table 13-1-Appendix 2 should be followed up by the investigator or designated personnel at the trial site as summarized below. Detailed information is outlined in Table 13-2-Appendix 2.

For the liver laboratory trigger:

- Repeating the liver function test (LFT) within the next week to confirm elevation.

These LFT repeats must be performed using the central laboratory if possible. If this is not possible, then the repeats can be performed at a local laboratory to monitor the safety of the patient. Repeats laboratory must then be performed at central laboratory as soon as possible. If a liver event is subsequently reported, any local LFTs previously conducted that are associated with this event must be reported on the Liver eCRF pages.

- If the elevation is confirmed, close observation of the patient will be initiated, including consideration of treatment interruption if deemed appropriate.

For the liver events:

- Repeating the LFT to confirm elevation as appropriate
- Discontinuation of the investigational drug if appropriate
- Hospitalization of the patient if appropriate
- A causality assessment of the liver event via exclusion of alternative causes (e.g., disease, co-medications)
- An investigation of the liver event which needs to be followed until resolution.

These investigations can include serology tests, imaging and pathology assessments, hepatologist's consultancy, based on investigator's discretion; obtaining more detailed history of symptoms and prior or concurrent diseases, history of concomitant drug use, exclusion of underlying liver disease. All follow-up information, and the procedures performed must be recorded on appropriate eCRF pages, including the liver event overview eCRF pages.

7.4 Reporting of study treatment errors including misuse/abuse

Medication errors are unintentional errors in the prescribing, dispensing, administration or monitoring of a medicine while under the control of a healthcare professional, patient or consumer (EMA definition).

Misuse refers to situations where the medicinal product is intentionally and inappropriately used not in accordance with the protocol.

Abuse corresponds to the persistent or sporadic, intentional excessive use of a medicinal product, which is accompanied by harmful physical or psychological effects.

Study treatment errors and uses outside of what is foreseen in the protocol will be collected in the dose administration record (DAR) eCRF irrespective of whether or not associated with an AE/SAE and reported to Safety only if associated with an SAE. Misuse or abuse will be collected and reported in the safety database irrespective of it being associated with an AE/SAE within 24 hours of Investigator’s awareness.

For more information on AE and SAE definition and reporting requirements, please see the respective sections.

Table 7-1 Guidance for Capturing the Study Treatment Errors Including Misuse/Abuse

Treatment error type	Document in Dose Administration (DAR) eCRF (Yes/No)	Document in AE eCRF	Complete SAE form
Unintentional study treatment error	Yes	Only if associated with an AE	Only if associated with an SAE
Misuse/Abuse	Yes	Yes	Yes, even if not associated with a SAE

7.5 Pregnancy reporting

To ensure patient safety, each pregnancy occurring after signing the informed consent must be reported to Novartis within 24 hours of learning of its occurrence. The pregnancy should be followed up to determine outcome, including spontaneous or voluntary termination, details of the birth, and the presence or absence of any birth defects, congenital abnormalities, or maternal and/or newborn complications.

Pregnancy must be recorded on the Pharmacovigilance Pregnancy Form and reported by the investigator to the local Novartis Drug Safety and Epidemiology Department. Pregnancy follow-up should be recorded on the same form and should include an assessment of the possible relationship to the study treatment.

Any SAE experienced during the pregnancy and unrelated to the pregnancy must be reported as an SAE.

7.6 Prospective suicidality assessment

The Columbia-Suicide Severity Rating Scale (C-SSRS) is a questionnaire that prospectively assesses Suicidal Ideation and Suicidal Behavior (Posner 2011). The C-SSRS must be administered at each visit, including unscheduled visits.

A validated version of the C-SSRS will be used to capture self-reported C-SSRS data via web-based interactive response system (eC-SSRS). The eC-SSRS uses a detailed branched logic algorithm to perform the C-SSRS patient interview, evaluating each patient’s suicidality ideation and behavior in a consistent manner. At the conclusion of each assessment, the investigator will receive a detailed eC-SSRS Findings Report via e-mail or fax. If the system

assesses the patient as having positive suicidal signs, the investigator will be immediately notified by either fax, e-mail and/or via telephone.

If, at any time after screening and/or baseline, the score is “yes” on item 4 or item 5 of the Suicidal Ideation section of the C-SSRS or “yes” on any item of the Suicidal Behavior section, the patient must be referred to a mental health care professional for further assessment and/or treatment. The decision on whether the study treatment should be discontinued is to be taken by the investigator in consultation with the mental health professional to whom the patient is referred.

In addition, all life-threatening events must be reported as SAEs. For example, if a patient answers “yes” to one of the questions in the Suicidal Behavior section, an SAE must be reported if the event was life-threatening. All events of “Non-Suicidal Self-Injurious Behavior” (question also included in the Suicidal Behavior section) should be reported as AEs and assigned the appropriate severity grade.

All SAEs relating to suicidal behavior must be reviewed by the Safety Management Team or early project teams.

8 Data review and database management

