5.6 Study completion and discontinuation

5.6.1 Study completion and post-study treatment

A patient will be considered to have completed the double-blind treatment epoch when the patient has completed Visit 199 in the protocol.

The patient's completion status will be recorded on the appropriate Study Phase Completion eCRF pages.

For all patients tapering off Control-IMP after study completion, an unscheduled visit has to be conducted after finishing the tapering off phase. At this visit, information about Control-IMP compliance, AEs, SAEs and concomitant medications have to be collected.

For all patients a safety follow-up visit (visit 201) should be conducted 4 weeks after the last visit or 8 weeks after the last IMP injection. The information to be collected at this follow up visit is outlined in Table 6-1.

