The investigator must also contact the IRT to register the patient's discontinuation from study treatment. If study drug discontinuation occurs because treatment code has been broken, please refer to Section 5.5.9. Patients who are prematurely withdrawn from the study will not be replaced by an equal number of newly enrolled patients. All patients receiving a daily dose of 75 mg or 100 mg topiramate (for at least one week) should perform a taper off phase for one week after discontinuation of study treatment. After the taper off phase an unscheduled visit should be performed to record control-IMP compliance, AEs, SAEs and concomitant medications.

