- 3 – Including prior prophylactic medication.
- 4 – Includes blood pressure, pulse and temperature.
- 5 – Patient brings to each visit for use at site
- 6 – To be completed during applicable study visits before study drug administration, where applicable.
- 7 – Should also be performed at unscheduled visits.
- 8 – SAEs will be collected after signing of the informed consent through the end of the Follow-Up Epoch (8 weeks after the last IMP injection). Non-serious AEs will be collected after randomization (Visit 101) through the end of the Follow-Up Epoch (8 weeks after the last IMP injection).
- 9 – Study drug is administered by study staff, during the applicable study visits, q.m., s.c..
- 10 – Oral study drug will be dispensed to the patient at the center during the applicable study visit for home application.
- 11 – Sites will access the Interactive Response Technology (IRT) System to register study early termination.
- 12 – Should be additionally performed at any visit if deemed necessary by the investigator due to AEs.
- 13 – Should be performed/registered by the investigator prior to dosing during DBTE.
- TD = Treatment discontinuation; PFS = Prefilled syringe; PSD = Premature subject discontinuation; X = Assessment to be recorded in the source documents and the clinical data base; S = Assessment to be recorded as source documentation only.

Table 6-2 Abbreviated schedule of assessments (ASA) for patients with Treatment Discontinuation (TD)

Visit number	V105-ASA	V108-ASA	V109-ASA	V110-ASA	V111-ASA	V199-ASA	V201-ASA ²
End of Week¹	4	8	12	16	20	24	28
Complete Physical Exam						S	
Brief Physical Exam	S	S	S	S	S		
Weight						X	X
Vital Signs ³	X	X	X	X	X	X	X
Chemistry/Hematology ¹²		X				X	X
Serum Pregnancy						X	
Urine pregnancy	S	S	S	S	S		X
ECG						X	
Clinical Outcomes (eDiary)	eDiary should be maintained						
SF-36 ⁴ (eDiary)	X	X	X	X	X	X	
HIT-6 ⁴ (eDiary)	X	X	X	X	X	X	
C-SSRS	X	X	X	X	X	X	
Concomitant Medications	X	X	X	X	X	X	X
Adverse Events ⁵	X	X	X	X	X	X	X
Serious Adverse Events ⁵	X	X	X	X	X	X	X
Follow Up Phase Completion form							X

1 – All study visit target dates are to be calculated from the Day 1 visit date, and all study procedures for a given visit should be completed in the same day.

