**2.1.1.3 Demographics and other baseline characteristics**

**Beck Depression Inventory II (BDI-II)**

The BDI-II is a 21-item questionnaire that assesses severity of depression with the recall period of two weeks, including the day of completion. Each item is scored from 0 to 3. The total score varies between 0 and 63 and can be categorized into 4 severity grades:

- minimal depression (0-13)
- mild depression (14-19)

- moderate depression (20-28)
- severe depression (29-63)

The BDI-II is completed once during the study at screening visit via eDiary. Moderate and severe depression belong to the study exclusion criteria.

Please refer to [BDI-II scoring](#) for scoring details.

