#### **Suicidal behavior**

- Cat. 6 - Actual attempt (non-fatal)
- Cat. 7 - Interrupted attempt
- Cat. 8 – Aborted or self-interrupted attempt
- Cat. 9 - Preparatory acts or behavior
- Cat. 10 - Suicide

The C-SSRS is administered at each visit, including unscheduled visits. Two versions depending on the type of visits will be used in this study: Screening and Since Last Visit. Please refer to [C-SSRS scoring](#) for scoring details.

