### 2.8.4.3 Columbia Suicide Severity Rating Scale (C-SSRS)

The number and percentage of subjects reporting any suicidal ideation or any suicidal behavior will be summarized descriptively by treatment group and by visit, for DBTE and for safety follow-up period, respectively.

Shift table of C-SSRS maximum severity of suicidal ideation/behavior compared to baseline will be provided by treatment group for DBTE and for safety follow-up period, respectively.

No statistical testing will be performed on C-SSRS.

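### Protocol Table 6-2 leaves the C-SSRS blank at the week 28 follow-up visit (V201-ASA), in conflict with Protocol 7.6 and with the follow-up C-SSRS tables planned in SAP 2.8.4.3

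*Protocol*

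**What the plan says.** Protocol 7.6 sets the general rule: "The C-SSRS must be administered at each visit, including unscheduled visits". The SAP restates it in its C-SSRS definition (2.1.1.5): "The C-SSRS is administered at each visit, including unscheduled visits".

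Patients who stop study treatment but remain in the study follow Protocol Table 6-2, which 5.6.2 applies to them up to the week 28 follow-up visit. Its columns are "V105-ASA V108-ASA V109-ASA V110-ASA V111-ASA V199-ASA V201-ASA", at weeks 4, 8, 12, 16, 20, 24 and 28. The C-SSRS row carries an X in the first six columns and nothing under V201-ASA.

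For the unscheduled visit after the topiramate taper, 5.6.1 (completers) says: "At this visit, information about Control-IMP compliance, AEs, SAEs and concomitant medications have to be collected". Section 5.6.2 (early discontinuation) says: "After the taper off phase an unscheduled visit should be performed to record control-IMP compliance, AEs, SAEs and concomitant medications". Neither list names the C-SSRS.

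SAP 2.8.4.3 plans, by arm, a by-visit summary of patients with suicidal ideation or behavior and a shift table of maximum severity against baseline. Both are to be produced "for DBTE and for safety follow-up period, respectively".

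**The concern.** The general rule and the visit table give different instructions for the same visit. Table 6-2 is what a site will have open for a patient who has stopped treatment. The opening of Protocol section 6 presents the two schedules as complete lists of assessments, and section 6.5 refers the reader to them for the timing of the C-SSRS. A site could therefore reasonably read the empty cell as meaning that the C-SSRS is not due.

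Two things are at stake. The first is the analysis. The SAP's follow-up C-SSRS tables would lack scheduled data from treatment discontinuers. That loss would be unequal between arms if discontinuation is unequal, and AE-related discontinuation is what the primary hypothesis compares. The second is the safety procedure. Under 7.6 a positive answer on the C-SSRS triggers mandatory referral, and at week 28 that trigger would not be applied to these patients.

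**Working it through.** No sample size or error-rate figure is involved. The check is a count of table cells and a comparison of sections.

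**1. Is the blank real?** Table 6-2 has seven visit columns. Rows compared:

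| Row in Table 6-2 | Marks, V105-ASA to V199-ASA | Mark at V201-ASA |
|---|---|---|
| Vital signs | 6 | yes |
| Concomitant medications | 6 | yes |
| Adverse events | 6 | yes |
| Serious adverse events | 6 | yes |
| Weight | 1 (V199-ASA) | yes |
| Urine pregnancy | 5 (blank at V199-ASA) | yes |
| C-SSRS | 6 | **no** |

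Four rows show seven marks. The urine pregnancy row keeps its blank at V199-ASA in place before the mark at V201-ASA. Empty cells therefore survived the conversion to text, and the C-SSRS blank is not a shifted row. The C-SSRS is scheduled at 6 of 7 visits.

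**2. How long is the gap?** The last scheduled C-SSRS is at week 24 and the follow-up visit at week 28: 28 − 24 = 4 weeks, one visit. For example, a patient who stops treatment at week 6 still has five scheduled assessments, at weeks 8, 12, 16, 20 and 24.

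**3. What reaches the SAP tables?** The visit windows in SAP Table 2.1.1.2-1 assign the week 24 assessment to the double-blind epoch (study days 155 to 182). It cannot fill the follow-up table. SAP 2.8 imputes no safety data. So if sites follow Table 6-2, a treatment discontinuer has no scheduled follow-up value and no entry in the follow-up shift table, which needs a post-baseline value from that period.

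The effect on the incidence table depends on the denominator, which 2.8.4.3 does not name:
- Under the general rule in SAP 2.1, missing values are left out of percentages, so these patients drop out of the denominator.
- Under the subject-incidence definition in SAP 2.1.1.5, the denominator is everyone who entered the period, so they would count as patients without an event.

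Under either rule, the arm with more discontinuers is affected more.

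**4. How many patients?** The readable text gives no discontinuation rate, so no count is offered. As a scale only: with 375 patients per arm (SAP 1.1), each percentage point of patients who stop treatment and stay in the study is 0.01 × 375 = 3.75 patients. With the 700 in the Protocol summary, split 1:1, it is 0.01 × 350 = 3.5. These are upper bounds per point, because footnote 2 of Table 6-2 lets V201-ASA be skipped in some cases.

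**The case against.** The strongest reply is that 7.6 is a mandatory rule covering every visit. Table 6-2 then contains a slip in one cell, and the C-SSRS remains due at V201-ASA. It can be added that the follow-up C-SSRS output is descriptive, with no testing planned, and that the double-blind tables keep discontinuers' data through week 24. All of this limits the consequence. It does not remove the conflict, because 5.6.2 directs sites to Table 6-2 for these visits.

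Several stronger readings are tempting, and the documents do not support them:

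- A reader might infer that early stoppers leave the study without a final suicidality check. They have scheduled C-SSRS assessments through week 24. Patients who leave the study altogether, rather than only treatment, get the Visit 199 assessments and a follow-up under Table 6-1 (5.6.2), so the empty cell does not govern them.
- A reader might infer that the post-taper visit goes without the C-SSRS. The lists in 5.6.1 and 5.6.2 are silent and exclude nothing, and 7.6 names unscheduled visits. A footnote to Table 6-1 also extends some assessment to unscheduled visits, but its row cannot be read. The list is the same for completers, so it does not single out early stoppers. For most of them the one-week taper ends well before week 28, with further C-SSRS visits in between.
- A reader might infer from "The BDI-II is completed once during the study at screening visit via eDiary" that the C-SSRS is the only mood instrument after baseline. The SF-36, with its mental health content, runs through V199-ASA. Adverse events are asked about at every visit, V201-ASA included.
- A reader might attach patient numbers by arm. These would rest entirely on assumed stop rates.

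**Conclusion.** The inconsistency is real, and small. Table 6-2 omits the C-SSRS at V201-ASA, against Protocol 7.6 and SAP 2.1.1.5, and SAP 2.8.4.3 plans follow-up tables that need those data. For patients who stop treatment but stay in the study, the last scheduled C-SSRS is at week 24. One visit and four weeks are uncovered.

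The consequence rests on two conditions: that sites follow the table rather than 7.6, and that V201-ASA takes place. Under those conditions these patients contribute no scheduled data to the follow-up C-SSRS tables, and the loss is larger in whichever arm has more of them. The primary and secondary analyses are unaffected. The conclusion is limited to Table 6-2, because the assessment rows of Table 6-1 are not readable and nothing is inferred from their absence.

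**What to change.** Reconcile Table 6-2 with Protocol 7.6 and SAP 2.8.4.3 by placing an X for the C-SSRS at V201-ASA. This follows the documents' own rule and gives the planned follow-up tables their data. If week 28 was left out on purpose, then 7.6, SAP 2.1.1.5 and SAP 2.8.4.3 need the matching exception instead.

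As an optional clarification, name the C-SSRS in the post-taper visit lists of 5.6.1 and 5.6.2, which 7.6 already covers as unscheduled visits.

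The cost is one table cell and, if wanted, two short wording additions. The follow-up visit, the electronic C-SSRS system and the planned analysis already exist. The added burden is one self-report per patient at a visit that takes place anyway.
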